RSSearch[®] Patient Registry Protocol

Sponsor: the Radiosurgery Society[®]

July 19, 2022

the
Radiosurgery
Society[®]

Table of Contents

1	Registry Title	3
2	Purpose	3
3	Objectives	3
4	Duration	4
5	Participants	4
6	Sponsorship	4
7	Patients	5
8	Forms.....	6
9	Data Recording.....	8
10	Patient Confidentiality	8
11	Security.....	9
12	Reporting	9
13	IRB/Ethics Review Committee Approval	9
14	Risks/Benefits	9
15	Reporting of Adverse Events	10
16	Appendix A: Institutional Review Board (IRB) and Ethics Review Committee Considerations.....	11
17	Appendix B: Sample Text for Patient Consent Form.....	12
18	Appendix C: Sample Registry Authorization form	14
19	Appendix D: Access to Data and Aggregate Reporting	17
20	Appendix E: Health-Related Quality of Life Questionnaires.....	21

RSSearch® Patient Registry Protocol

1 Registry Title

RSSearch® Patient Registry

The RSSearch® Patient Registry is an international, multi-center ongoing database designed to track utilization of all available stereotactic radiosurgery (SRS)/stereotactic body radiation therapy (SBRT) and Spatially Fractionated Radiation Therapy (SFRT – like GRID and LATTICE radiation) systems, treatment practices and outcomes to help determine, over time, the most effective use of these systems in management of patients with life threatening tumors and other diseases.

The RSSearch® Patient Registry meets all Health Information Portability and Accountability Act (HIPAA) requirements regarding patient privacy and transmission of protected patient information.

Participant access to data entered into the RSSearch® Patient Registry will be limited as follows:

- Each clinical site will have full access to all data entered by that clinical site
- Each clinical site may have access to some reports using aggregate data, if created by the Radiosurgery Society® (RSS). Each clinical site may petition for access to aggregate data via the process outlined in Appendix D: Access to Data and Aggregate Reporting.

Sponsor

the Radiosurgery Society®

Primary Contact

[name]
Executive Director
the Radiosurgery Society®
Email: [contact]
[contact]

2 Purpose

The RSSearch® Patient Registry is a database designed to standardize the collection of data on the use of SRS/SBRT/SFRT systems in everyday practice. Data to be recorded includes:

- Characteristics of patients who are selected for these treatments
- Treatment locations, disease diagnoses and lesion descriptions
- Treatment goals
- Treatment plans and delivery information
- Outcomes data
- Patient-reported quality of life questionnaires (if desired by the participating sites and approved by their Institutional Review Board (IRB)). See Appendix E for list of available health-related quality of life questionnaires.

The registry design including data collection forms were designed by a board of Clinical Advisors who are active users, including physicians, physicists, nurses and site administrators. The RSSearch® Patient Registry uses widely accepted standards for disease classification, treatment side effects and results and validated quality of life measures.

3 Objectives

Objectives of the RSSearch Registry include the following:

RSSearch® Patient Registry Protocol

Version Date: 7/19/2022 Version 1.1

- Allow participants to record information about usage of the SRS/SBRT/SFRT systems in everyday practice, including patient characteristics and disease information, treatment plans and outcomes
- Allow participants to record information useful for their own SRS/SBRT/SFRT business reporting including utilization
- Provide participants with ready access to data for publication of their own SRS/SBRT/SFRT experience and as a tool for establishing collaborations with other participating sites
- Facilitate quality improvement efforts for individual treatment providers
- Provide participants the opportunity to collect quality of life data and other patient-reported outcomes
- Understand the effectiveness of different treatment plans for different types of lesions, diseases and treatments
- Provide comparative patient outcomes data to facilitate appropriate and successful use of the SRS/SBRT/SFRT system
- Collect information that may be useful for reimbursement

The RSSearch® Patient Registry is not a clinical trial or study. It is listed on www.clinicaltrials.gov and described as an observational patient registry (ClinicalTrials.gov Identifier: NCT01885299).

Information entered into RSSearch is already being collected as part of the medical record for patients at participating sites.

4 Duration

The RSSearch® Patient Registry will be an ongoing effort. This Registry began in 2005, as the ReCKord CyberKnife Registry and these CyberKnife patients remain embedded in RSSearch.

5 Participants

All clinical sites performing SRS/SBRT/SFRT treatment procedures of any kind will be invited and encouraged to participate in the Registry. Participation is voluntary, but Principal Investigators must be an active member of the Radiosurgery Society. There is no compensation for participation in the Registry, either to patients or to participating sites.

All sites participating in the Registry will be required to have a signed Data Use Agreement (DUA) or similar agreement with the Radiosurgery Society and submit this protocol to their Institutional Review Board (IRB) or Ethics Committee Review; this will expand the opportunities for collaboration and publication.

Sites will be required to comply with their own institution's IRB or Ethics Committee Review practices for ongoing review and approval.

Participating sites are responsible for sending the RSS Administrator documentation providing proof that they have received and/or have updated IRB or Ethics Committee Review approval.

6 Sponsorship

RSSearch resides under the auspices of the Radiosurgery Society and is funded partially through the membership fees of the RSS. An annual maintenance fee is required of all participants in RSSearch to cover costs for data storage, hosting fees, registry quality assurance (QA) and security checks.

The Radiosurgery Society® is a multidisciplinary non-profit organization aimed at advancing the science and clinical practice of radiosurgery. (See www.therss.org for additional information)

Objectives of the Radiosurgery Society® include:

- Improve results achieved in the field of Stereotactic Radiosurgery (SRS), Stereotactic Body Radiation Therapy (SBRT) and Spatially Fractionated Radiation Therapy (SFRT) by promoting scholarly exchange among the clinical users.
- Share detailed clinical information pertaining to SRS, SBRT and SFRT to promote protocol development.
- Encourage and enhance SRS, SBRT and SFRT techniques in the worldwide medical community and among healthcare providers and patients.

7 Patients

All patients of any age who are screened for potential SRS/SBRT/SFRT treatment are eligible to be entered into the RSSearch Registry. Some basic information including referral source, disease location etc., will be entered for any *patient who is screened* for SRS/SBRT/SFRT System treatment. Additional detailed demographic, diagnostic, treatment plan and follow up data will be entered on *patients who are selected* for one or more of these treatments. Patients who are selected and treated with SRS/SBRT/SFRT approaches will have data about their health status collected over the long-term, as long as they are considered candidates for follow-up.

There are no specific inclusion/exclusion criteria. The RSSearch® Patient Registry does not require specific tests or measures. Data that is collected in the normal course of a patient's treatment and follow up are entered into RSSearch.

There are no established endpoints for the RSSearch (as there are, for instance, for a Clinical Study); however, specific measures are recorded before and after treatment to determine outcomes of various SRS/SBRT/SFRT treatment approaches for different diseases.

All prospective patients must sign or have signed an informed consent form prior to their data being entered into the RSSearch® Patient Registry.

Initial entry of retrospective patient data may be considered under a Waiver of Authorization.

A Waiver of Authorization may be applicable for the following reasons:

- Risk to subject privacy is minimal
 - Procedure data is de-identified via the use of a unique identification number (ID) that will be created and known only to the participating site
 - Only four of the 18 variables considered protected health information (PHI) are necessary for use of RSSearch, specifically dates (admission, discharge, service dates, date of death), age (birthdates not collected), zip code and patient e-mail address (collected only if an individual site and their respective patients wish to use the Patient Portal feature of RSSearch, and then the email is visible only to the participating site).
 - The dates are important for understanding the data including, if and when:
 - Any adverse events occurred during and after the procedure
 - Key cancer outcomes including survival

- If participating sites are using the Patient Portal feature, the patient e-mail will allow the patient to securely log-in to the Patient Portal and access and complete assigned quality of life questionnaires.
- Obtaining informed consent from patients who have already had a procedure and may not be returning for follow-up at a treating center performing the procedure may not be practical
- Obtaining informed consent may also inhibit a participating site's ability to completely characterize their patient population over time, practices associated with use of their SRS/SBRT/SFRT systems and long term outcomes

Retrospective data is marked as such in the database and can be separated for data analysis and publication purposes.

If Informed Consent is not obtained for initial data entry of retrospective patients and if the patient returns for follow-up or if follow-up data is otherwise obtained, Informed Consent can be obtained at follow-up.

If practical, obtaining Informed Consent from both retrospective and prospective patients is highly encouraged.

8 Forms

The RSSearch Registry includes the following forms and is available upon request:

- Screening Form
- Treatment Plan Form
- Follow-up Form
- Quality of Life Questionnaires

The registry contains both required and optional data fields, but it is highly recommended that all data fields, including required and optional fields be entered into RSSearch.

Screening Form

On the Screening Form, information is entered about any patient who is screened for treatment.

A new Screening Form is initiated and used for:

- New patients who have not previously been treated with SRS/SBRT/SFRT
- Existing patients who have previously been treated with SRS/SBRT/SFRT and
 - Have a recurrence or need for additional treatment at a previously treated target location, or
 - Have a new target treatment location or locations
- Existing patients who have previously been screened, but not treated by SRS/SBRT/SFRT
- Patients who are screened and not selected for SRS/SBRT/SFRT

If a patient has more than one target treatment location that will be treated during a single treatment period, details on these individual treatment locations will be recorded on the Screening Form.

If patients are screened and *not* selected for SRS/SBRT/SFRT, some basic information is entered including treatment location, referring physician and the reason why one of these systems was not selected for this patient at this time.

If patients are screened and selected for SRS/SBRT/SFRT treatment, the basic information mentioned above as well as the following additional information is entered; relevant patient characteristics and health status; detailed diagnostic information; and some information on reimbursement.

Treatment Plan Form

The Treatment Plan Form is filled out for every patient selected for SRS/SBRT/SFRT treatment. The design of the Treatment Plan Form follows typical treatment approaches, where a single treatment plan may be used to treat one or more lesions and multiple treatment plans may be used to treat a single target location. Clinicians will record one or more treatment plans and lesion details on a single Treatment Plan Form for any particular treatment period.

General Treatment Planning Systems (TPS) information can be digitally uploaded into RSSearch using an automated feature in VisionTree Optimal Care (VTOC) database platform (VisionTree, San Diego, CA, www.visiontree.com) the developer of the database platform used for RSSearch. This feature reduces the amount of duplicate data entry by participating sites while providing key information to meet the RSSearch Patient Registry objectives.

SRS/SBRT/SFRT systems not supported by system manufacturers may require manual entry of certain treatment planning information.

Treatment Plan Forms will be linked electronically within the database to patients, target treatment locations and lesions to assist with proper tracking for outcomes analysis.

Follow-Up Form

The Follow-Up Form is used to document the result of each treatment plan.

Follow-Up Forms are used at intervals determined appropriate by individual clinical sites. Data is recorded after patients attend regularly scheduled follow-up appointments. Patients are expected to be followed as long as they are deemed candidates for follow-up.

Follow-Up Forms will be linked electronically to patients and target treatment locations, lesions and treatment plans to assist with proper follow up and outcomes analysis.

Patient Quality of Life and other Patient-Reported Outcomes Forms

The patient quality of life questionnaires are optional and may be used if your institution wishes to collect these data. However, we are actively encouraging participants to collect quality of life data. The patient quality of life forms have been reviewed by the RSSearch Advisory Committee and are available and visible in the "Patient To Do's" Tab of the Registry. Many of the patient quality of life questionnaires are standard forms, validated and used to collect these kinds of data. A list of available quality of life and patient-reported outcomes forms are in Appendix E.

There are two approaches to reporting patient quality of life-data: 1) Via a secure VisionTree Patient Portal which automates the process by using the patient's email and your institution's selected forms of

interest. Patients will only be able to access their specifically assigned QOL forms. 2) Centers can manually enter patient-reported outcomes data through the Medical Team Portal. Forms can be printed from the VisionTree system, completed by the patient and then the medical team can enter the information directly into RSSearch.

9 Data Recording

The data recorded in the course of this registry will be documented on electronic case report forms (eCRFs) within a secure web-enabled software application. An independent medical software and web management company, VisionTree, San Diego, CA (www.visiontree.com), Inc. has designed and is managing the database and maintaining a HIPAA compliant system.

The system requires all information that is transmitted across the Internet be encrypted via Hyper Text Transfer Protocol Secure (HTTPS). To help avoid unauthorized usage, an automatic log-off feature is utilized after an extended period of user inactivity. A role-based security model is implemented to restrict access to various segments of the system (i.e. reports, screens, and site-specific data, along with other identified restricted information). In addition, the user interface and application components are stored behind an industry standard firewall with all outside communication closed except HTTP, HTTPS and Virtual Private Network (VPN) communication, while the database is only accessible via the internal network and VPN access. The system is physically housed within a HIPAA compliant facility including network redundancy for data availability, 24/7 network monitoring, multilevel access control requiring Badge/Photo ID and biometric access screening, internal and external video monitoring, fire protection, and disaster and environmental controls. The server and network updates are managed by VisionTree. The system data is backed up daily.

10 Patient Confidentiality

A unique patient identification number created and known only to your participating facility should be utilized in RSSearch and not a Medical Record Number. This data field is considered a “private” field and available only to the clinical site entering that data. The patient identification number will be used only as required for registry operations, specifically:

- To assist in enabling the digital import of treatment plan data from various Treatment Planning Systems, automatically and accurately linking the data
- To assist in enabling the digital import of data currently being collected in electronic form by participating clinical sites
- To make it easier for individuals at participating clinical sites to find a specific patient to enter additional data, to modify previously entered data and to record follow up data

As an additional security measure, a randomly generated patient ID is generated by VisionTree and linked to the unique patient ID created by the individual sites. This randomly generated ID can be used by VisionTree and the RSS to communicate with you if necessary, about specific patients. See Section 9 above to see how the limited PHI entered into RSSearch will be managed and protected by the software application and services provided by VisionTree.

Some payer and payment information is being collected to help gain insight into reimbursement of SRS/SBRT/SFRT treatment for different diagnoses by different health plans. Individual patient health plan numbers are *not* included in the database.

Patient email addresses may be collected by individual sites to allow patients to access the Patient Portal in order to view and complete select Quality of Life forms. If email addresses are collected for this purpose, these emails are only visible to the individual site and will be protected by the software application processes put in place by VisionTree.

All patient data will be de-identified prior to use for research and analysis. If and when comparisons of aggregate data are made, no specifically identified patient-to-patient, physician-to-physician or geographic comparisons of data will be performed.

11 Security

Participants will be required to enter a unique username and password to access the RSSearch Patient Registry. No sharing of usernames and passwords will be allowed.

If a clinical site determines they need written copies of RSSearch Data Collection Forms, these should be managed in accordance with data protection regulations by that clinical site.

12 Reporting

Participants may routinely access reports of their own individual center's data and are free to publish their own data at any time. The particular research and methods must be evaluated for scientific merit and ethical propriety by their own institutions. Publications or presentations that result from the RSSearch Registry should be acknowledged accordingly.

The RSSearch Registry Review Committee (RRRC) composed of SRS/SBRT/SFRT users may review and release de-identified aggregate data as deemed appropriate for publication. Any individual participating site may choose to have their data included or excluded in the released aggregate data, but because aggregate data will not contain any identifiers, either patient, physician or site, all participating sites will be encouraged to include their data to increase the value for educational purposes. Participating sites/clinicians and the RSS may submit requests for aggregate data for publication to the expert review panel. Please see Appendix D for details on aggregate reporting.

13 IRB/Ethics Review Committee Approval

IRB or Ethics Review Committee review and approval is required to participate in the RSSearch Registry (see Appendix A for review considerations).

Patient Informed Consent

Obtaining Patient Informed Consent for prospective patients being entered into the database is required and is highly suggested for retrospective patients; since increasingly, peer reviewed publications require Informed Consent for submitted research. A sample Patient Consent Form is attached in Appendix B. For institutions that require a patient research authorization to collect patient data prospectively, a sample Patient Authorization Form is attached in Appendix C.

14 Risks/Benefits

There are no specific risks to patients of having limited patient information collected in a central database. Information entered into RSSearch is currently being collected as a standard part of patient care and follow up.

The benefits may include improved follow up for individual patients by participating sites and improved understanding of the use and results of SRS/SBRT/SFRT treatment for all patients.

15 Reporting of Adverse Events

The RSearch® Patient Registry provides a means on the Follow-Up Form for participating sites to indicate if the patient is experiencing any unexpected side effects or adverse events (AE) that can be attributable to SRS/SBRT/SFRT treatment. Reported adverse events will be graded on a scale of 1-5 as defined by the published standard Common Terminology Criteria for Adverse Events (CTCAE) v5.

Participation in RSearch with its AE system does not in any way replace the responsibilities of clinicians or sites in reporting adverse events related to any treatment in accordance with all applicable laws and regulations including notifying the manufacturer of the associated SRS/SBRT/SFRT device, or medical complaints associated with SRS/SBRT/SFRT treatment as soon as possible.

16 Appendix A: Institutional Review Board (IRB) and Ethics Review Committee Considerations

Aspects to consider in determining what type of review (expedited or full board) application to use include:

1. The RSSearch® Patient Registry is not a clinical trial or study, and no investigational device exemption (IDE) is required for use of the various SRS/SBRT/SFRT Systems.
2. Data entered into RSSearch are observational outcomes data, which are already collected as part of the medical records for patients undergoing SRS/SBRT/SFRT treatment.
3. A unique patient identification number (not medical record number) is recorded at the site level, is only available to the respective site, and is used for the following purposes:
 - a. To match the various Treatment Planning System data
 - b. To assist in long term follow up at the participating site
 - c. For registry operations
4. Physician-specific data will only be available to the respective site.
5. The RSSearch® Patient Registry is being managed in a secure environment by VisionTree®, San Diego, CA, an independent developer of web-based registries.

19 Appendix D: Access to Data and Aggregate Reporting

Overview

This guideline provides information on the specific and accepted professional use of data and database-derived information of the RSSearch® Patient Registry.

Use of Data

Participants: RSSearch® Patient Registry “Participants” may consist solely of one or more physicians, physicists, nurses and site administrators, plus their hospital or center, at the physician’s election, who engage in the process of collecting clinical practice data and utilization of data-base derived information.

Participants may routinely access reports of their own individual center’s data and are free to publish their own data at any time. The particular research and methods must be evaluated for scientific merit and ethical propriety by their own Institutional Review Board or Ethic Review Committee.

Any individual participating site may choose to have their data included or excluded in the released aggregate data, but because aggregate raw data will not contain any identifiers, either patient, physician or site, all participating sites will be encouraged to include their data to increase the value for educational purposes. Participating sites/clinicians and the RSS may submit requests for aggregate data for publication for expert review panel.

Registry Administrator: The RSSearch® Patient Registry Administrators are the RSS employees, who are responsible for managing the development and maintenance of the registry. The responsibilities of the Administrators include:

- Oversee the management, development and maintenance of the database
- Providing participants with the most recent updated registry protocol, sample consent form and supporting materials for IRB, Ethics Review Committee or regulatory agency equivalent submission
- Acting as a liaison between the participants and the database vendor
- Creating and editing Data Collection Forms
- Notifying the database vendor of new participants or changes user access
- Coordinating database training
- Create and distribute timely reports of limited aggregate data under advisement of the RRRC
- Review and process applications for access to aggregate data
- May create, distribute and report on aggregate data and Quality Assurance and Performance Improvement studies with prior approval by the RSSearch® Patient Registry Review Committee (RRRC)

The Administrator will have read only access to de-identified registry data. All physician and specific patient identifying information will be restricted and not visible to the Administrator.

Aggregate Data Reporting: The RSSearch® Registry Review Committee (RRRC) will periodically review opportunities for presenting topline aggregate data to all participants via the Registry.

Access to data for publication and presentation: Data entered into the registry is available for research and publications. Clinical research on aggregated data may be used to produce one or more of the following forms of reporting and dissemination of information: abstract, scientific meeting presentation,

RSSearch® Patient Registry Protocol

Version Date: 7/19/2022 Version 1.1

manuscript for publication in the medical literature. Patient identifying information will remain confidential.

All publications will include reference to all participating RSSearch® sites. Researchers will be provided assistance in getting permission to be named in a publication by the RSSearch Administrator.

RSSearch® Registry Review Committee (RRRC):

The RRRC consists of clinicians with extensive SRS and SBRT experience that have been selected by RSS Board of Directors. The RRRC evaluates the proposals based on originality, interest and benefit to the entire SRS and SBRT community and feasibility (as defined by availability of data in the aggregate database).

All persons interested in publishing RSSearch® aggregate data must submit their proposal for publication and request for data analyses to the RRRC using the RSSearch® Request For Use of Aggregate Data Form (see Attachment D.1). **The Radiosurgery Society®** will submit requests for aggregate data for publication to the RRRC. The RRRC will review individual applications for aggregate data release. There is no fee to submit an application for RRRC.

As indicated above and throughout the document, no physician, patient, or site identifying information is available or will be made available in granted requests for aggregate data. Site identifying information will be provided to the Radiosurgery Society for purposes of aggregate study requests and for conducting quality assurance of the database.

RSSearch® Data Request Form for Use of Aggregate Data:

Eligibility Criteria for Participating Centers

(The RSS will not be held to below criteria)

- Enter > 50 patients into RSSearch® annually
- Principal Investigator must be an RSS member
- The RSS will not be held to this criterion

Submission Requirements

Please attach each of the following with your RSSearch® Request For Use of Aggregate Data Form:

- Copy of IRB approval letter for use of RSSearch® at your institution
- Curriculum vitae of the principal investigator
- The RSS will not be held to this criterion

General Information

Submit Appendix D: Access to Data and Aggregate Reporting to the RSS RSSearch Administrator at [contact] You will receive a letter regarding the status of your request within 30 business days. Requested custom aggregate data report will require a minimum of 2 weeks to generate.

Request For Use of Aggregate Data Form

Date of Submission (mm/dd/yy):	
Name of Organization:	
Project Title:	
Principal Investigator:	
Co-Investigators:	
Corresponding Contact Name:	
Contact Title:	
Contact Telephone Number:	
Contact E-mail Address:	
Contact Address: City, State, Zip:	

Project Description

Project Start Date (mm/dd/yy):	
Project End Date (mm/dd/yy):	
Type of Research Project:	 Prospective Study  Retrospective Analysis  Technical Study  Other
If "Other," please explain nature of project:	
What is the research question being asked?	
What is the background or rationale for the research question? (if needed, please attach as a separate page to application)	
Patient Inclusion/Exclusion Criteria:	

Data Requested

Description of patient population to be analyzed:	
Time frame to be studied:	
List exact data variables requested (i.e. pathology, treatment planning)	

information, outcome, reimbursement, etc.): If the request is not self-evident, write a summary of the request and/or instructions on data output (e.g., table specifications, sample tables).	
Deadline for receipt of data (mm/dd/yy):	

Data Use

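### Does barring identifiers from released aggregate data stop requesters from counting patients and allowing for site?

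*Protocol*

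**What the plan says.** Section 12 (Reporting) lets the registry review committee act on pooled data: it "may review and release de-identified aggregate data as deemed appropriate for publication". The same section gives the reason why sites should feel free to contribute: "because aggregate data will not contain any identifiers, either patient, physician or site". Appendix D, under Use of Data, has almost the same sentence with one word added: "because aggregate raw data will not contain any identifiers, either patient, physician or site". Later in Appendix D the rule returns in different terms: "As indicated above and throughout the document, no physician, patient, or site identifying information is available or will be made available in granted requests". The next sentence sets out what the sponsor itself receives: "Site identifying information will be provided to the Radiosurgery Society for purposes of aggregate study requests".

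The request form in Appendix D points to two kinds of output. It tells the applicant to "List exact data variables requested", and where the request is not self-evident it invites a summary or "instructions on data output (e.g., table specifications, sample tables").

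No section says whether a random code without an accessible key may travel with a release.

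**The concern.** Registry records are nested. Under Section 8, a patient who comes back with a recurrence or a new target gets a new Screening Form, one location may be treated under several plans, and follow-up is recorded for each plan. Patients are in turn grouped within sites.

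Suppose an extract went out with one row per record and no code for patient or site. The recipient could count records as patients, could not cluster on the patient, and could not allow for site. Standard errors for pooled rates and for contrasts between sites would tend to be too small. Pooled data serve the Section 3 objectives of learning how well different treatment plans work and of comparing outcomes, so this would matter. No analysis plan written afterwards could restore a key that the release had removed.

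**Working it through.** The Protocol states no sample size, power, error rate or event count that bears on this point, and Section 7 says there are no established endpoints. There is therefore no figure to reproduce. The check is a reading of the text, followed by an illustration of scale.

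**1. Does the rule forbid codes?**

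- Section 7 describes procedure data as de-identified by means of a unique ID known only to the site. A coded number is the tool of de-identification there, not a breach of it.
- Section 10 describes a second, randomly generated patient ID that the database vendor and the Society may use. Appendix D limits the Society's administrators to de-identified data and hides specific patient-identifying information from them. The two statements fit together only if the random ID is not regarded as identifying.
- The later Appendix D statement presents itself as a summary of what came before, and it speaks of identifying information rather than identifiers.

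The three statements are best read as one rule against identifying people and sites. For patient codes the text leans clearly that way. For site codes it is less explicit.

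**2. Are row-level data released?**

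- For: Appendix D uses the word *raw*, and the form asks for exact variables.
- Against: Appendix D also speaks of a request for data analyses, of limited aggregate reports and of a custom aggregate report, and the form mentions table specifications.

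The position is unclear.

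**3. Who can deal with the nesting?**

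Section 8 links treatment and follow-up forms to patients, and gives outcomes analysis as a purpose of the link. Appendix D gives the Society site identity for aggregate study requests. The Society therefore has the means to reduce records to patients and to cluster by site before release. Some repetition is also absorbed at entry: locations treated in one period share a Screening Form, and the plans and lesions of one period share a Treatment Plan Form. Repeats across treatment periods and follow-up visits remain.

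**4. Scale, if codes were withheld from row-level data**

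With equal clusters of size m and correlation ρ, the design effect is DE = 1 + (m − 1)ρ. An interval that ignores clustering has coverage 2Φ(1.960/√DE) − 1. Coverage of 90% corresponds to DE = (1.960/1.645)² = 1.420, so the break-even correlation is 0.420/(m − 1).

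| Cluster | m | Break-even ρ |
|---|---|---|
| Site | 51 | 0.420/50 = 0.0084 |
| Site (assumed size) | 10 | 0.420/9 = 0.047 |
| Patient, 2 records | 2 | 0.420/1 = 0.42 |
| Patient, 3 records | 3 | 0.420/2 = 0.21 |

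The figure of 51 is the smallest whole number that meets the criterion "Enter > 50 patients into RSSearch® annually". That criterion applies to centres that request data. It does not give the size of contributing sites.

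For a nominal 5% test of a site-level factor, the actual error is 2[1 − Φ(1.96/√DE)]. With m = 51 and assumed ρ of 0.01, 0.05 and 0.10, DE is 1.5, 3.5 and 6.0, and the error is about 11%, 30% and 42%. For a comparison between patients with 2 records each and assumed ρ of 0.5 and 0.8, DE is 1.5 and 1.8, and the error is about 11% and 14%.

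With one record per patient, DE = 1 and there is no patient-level loss. For a contrast made wholly within sites the variance factor is 1 − ρ, so the naive interval is not too narrow.

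**The case for a change.** The strongest case for a change is that this is a release rule, not a modelling choice. It stands in the document that sites submit for ethics review, and it is offered to them as the reason to include their data. Taken at its word, *any identifiers* could cover a random code. The only stated use of the random patient ID is communication with sites. A requester could ask for a coded key on the form, but the Protocol gives the committee no express basis for granting or refusing it. Nor does it say that the Society will reduce records to patients or cluster by site itself.

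Some of this stands. The text is silent on codes, the silence is more complete for sites than for patients, and the arithmetic shows that ignoring site can matter at small correlations. But silence is not a wrong rule, and the contents of an extract are commonly settled in the request or in the data use agreement, which is not shown.

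The fuller remedy is also not cheap. Zip code and service dates are registry fields, and beside a site code they could reveal where a site is. Guarding against that means limiting those fields and pooling small sites, which gives back part of the site adjustment. Contributing sites would have to be told, and ethics bodies might need to be notified. That is a trade-off between privacy and detail that the sponsor may reasonably settle project by project.

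**Conclusion.** No change to the plan is needed. The Protocol leaves unsaid whether non-identifying codes may accompany a release, but it states no wrong number, test or rule, and its three statements are best read as one. Harm would require two things together: the literal reading of *identifiers*, which the Protocol's own usage disfavours, and row-level output, which the text neither confirms nor excludes. Summary tables, extracts with one row per patient used for patient counts, and analyses that the Society clusters before release are unaffected.

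No actual size of effect can be given. The break-even values rest on equal cluster sizes and on assumed numbers of patients per site and records per patient. They describe clustered data in general, not this registry. An analyst who needs patient and site structure can ask for a coded key, for one row per patient or for a clustered analysis on the request form. If the text were being revised for another reason, wording the rule consistently in terms of identifying information would be tidier, but no analysis depends on it.
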